Outcomes will be collected in the EHR at baseline and 3-month follow-up and for a subset of Veterans surveys will be administered at baseline with follow up points at 3, 6, 9, and 12 months. The primary outcomes (PROMIS pain interference and physical function) and secondary outcome (PROMIS sleep quality) will be captured in templated progress notes in the VA medical record for participants (n = 1,680) using PROMIS short form instruments (4 items per scale). A subset of these same participants (n=848) will be consented for the additional survey data collection. These additional data will be used in the secondary and exploratory analyses; and the measures include more detailed patient reported outcomes on pain associated distress, physical function, and health care utilization as well as longer term follow-up.

Care Pathways and Duration

The Integrated Care Pathway (ICP) includes both on-site physical therapy (PT) services (delivered by PT providers at each participating VA clinic) and centrally-delivered services via telehealth. The ICP will be initiated by a referral from a provider at a participating primary care clinic. The first step of the ICP is contact by the central delivery provider to explain the ICP, determine preferences in delivery mode for centrally-delivered services (telephone vs video) and initiate onsite PT services. Onsite PT services will include a physical examination, and pain modulation treatment as determined by the provider that could include manual therapy or electrotherapy and capture of baseline data on pain and function. This first step will consist of a maximum of 2 on-site PT visits and it will take 2 weeks. The second step of the ICP will last 6 weeks, with patients receiving telehealth (i.e. telephone or video) calls for home physical activity instruction. The calls are will be conducted by centrally located Durham VA providers.

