1. STUDY OBJECTIVES

1.1 Primary Objective

Examine the effectiveness at 3 months of two care pathways for LBP: 1) an integrated care pathway (ICP) and 2) a coordinated care pathway (CCP). We will test the central hypothesis that the ICP will reduce pain interference with normal activities and improve physical function, as measured by PROMIS Short Form scores when compared to the CCP.

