9.2 Sample Size and Randomization

In **Table 8** below we present a range of minimum detectable effect size differences for the primary outcomes of Pain Interference or Function Scores for both the administrative sample (N=84 per clinic) and survey sample (N=42 per clinic) for 16 clinics (8 clinics randomized to each arm) for Aim 1. Sample size calculations for the cluster randomized design were based on the net difference between the two conditions across baseline and 3-months follow-up.⁵⁰ We assumed over time correlations of 0.50 for both patients (based on data from the [name] et al. pilot study³³ and summary data available for Durham VA clinics, intraclass correlation coefficients (ICC) of 0.01, 0.02, and 0.05 to account for clinic clustering, and also adjusted for the potential group-level randomization of up to 4 stratification variables as baseline covariate adjustments where we conservatively assumed no reduction in either group or subject level variance components. For all calculations, the type-I error is 2.5% to account for the multiple primary outcomes and power is conservatively assumed to be 90% to guard against deviations from assumptions. The number needed at baseline (N_b) is based on an attrition rate of 20%. Note in the **below Table 4** that the scenarios above lead to having adequate power to detect a medium effect size for the primary outcomes for both the administrative and survey samples.

Table 8. Minimum detectable effect size differences for 90% power, alpha of 0.025 and ICC of 0.01, 0.02, and 0.05 for administrative outcome (n=84 per clinic) and survey outcome (n=42 per clinic)

Number of clinics per condition	Number of patients per clinic needed at post-intervention follow-up (Total N)	Minimum Detectable Effect Size Difference ICC=0.01	Minimum Detectable Effect Size Difference ICC=0.02	Minimum Detectable Effect Size Difference ICC=0.05	Number of patients per clinic needed at baseline with 20% attrition (Total N_b)
8	42 (N=672)	0.37	0.42	0.55	53 (N_b =848)
8	84 (N=1344)	0.30	0.36	0.50	105 (N_b =1680)

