The standardized effect sizes⁵¹ that we are powered to detect range from 0.30 to 0.50 for the primary outcomes on the administrative sample. This range maps to differences of approximately 2.4 to 5.0 points in the PROMIS Pain Interference score between arms assuming standard deviations in the range found in the pilot study from [name] et al.³³ These magnitude of differences have been reported to be clinically relevant.⁵² Similarly for the survey sample, the range of effect size differences we can detect map to differences of approximately 3.0 to 5.5 points between arms.

For AIM 2, the subgroup analyses of the primary outcomes in the administrative sample, if we assume an even distribution of a binary moderator (e.g. opioid use), our effective sample size for detection of moderation is a quarter that for the main effect analysis yielding an effective sample size of n=336 (21 per clinic).⁵³ For the moderator interaction effect, we can detect medium to large effect size differences over a range of assumptions (**Table 9 below**), which allows for prudent exploration of treatment moderation.

Table 9. Minimum detectable effect size differences by a binary moderator for 90% power, alpha of 0.025 and ICC of 0.01, 0.02, and 0.05 for administrative sample.

Number of clinics per condition	Number of patients per clinic needed at post-intervention follow-up (Total N)	Minimum Detectable Effect Size Difference ICC=0.01	Minimum Detectable Effect Size Difference ICC=0.02	Minimum Detectable Effect Size Difference ICC=0.05	Number of patients per clinic needed at baseline with 20% attrition (Total N _b)
8	21 (N=336)	0.48	0.53	0.63	27 (N _b =432)

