
Secondary Analyses

We will assess differences in proportions of “responders” between treatment arms for each of the primary outcomes. A “responder” will be defined as achieving 30% improvement in pain interference or function scores at 3 months follow up.⁵⁸ Responder status for those missing outcome data will be estimated using best linear unbiased predictors from the hierarchical linear model⁵⁹ so that those missing observed follow up data will be included.

We will use a generalized linear mixed model with a logit link function to compare differences in responder status between arms where the main predictor of interest will be treatment arm adjusting for clustering of VA clinic either with random effects or by conditioning.^{55,60,61} As a sensitivity analysis to explore responder cut points of pain interference and function measures, we will compute cumulative proportion responder analysis graphs.⁶²

Secondary outcomes of sleep, opioid use, and health utilization (including chronic opioid usage) will also be obtained administratively on all eligible subjects. The sleep PROMIS measure is a continuous outcome that will be assessed at baseline and 3 months and similar modeling procedures as described for the primary outcomes will be used. Opioid use will be examined in two ways, one as a binary variable based on whether a chronic opioid user or not at baseline and 12 months and second using a continuous measure of morphine equivalents for opioid dose at baseline and 12 months.⁶³ For the dichotomous outcomes, we will use a generalized linear mixed model with a logit link function where the main predictor of interest will be treatment arm and will include baseline opioid use status (chronic or not chronic) adjusting for clustering of VA clinic either with random effects or by conditioning.^{55,60,61} For opioid morphine equivalent dose, we will fit a similar model as was described for the primary outcomes except the follow up time point in the model will be for 12 months. For imaging and ED utilization, we will assume a count-like distribution for the number of ED visits in the 12 months of follow up and will use generalized linear mixed model for count variables.⁵⁵

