10. MEASURES AND DATA COLLECTION

Outcome measures and timing of collection is summarized in **Table 10**. The data collection process is explained in subsequent sections.

Table 10. Summary of Measures.

Outcome Variable	Definition	Data Source	Baseline	3 months	6 months	9 months	12 months
Pain and Pain Impact Measures							
Pain Interference	PROMIS SF- 4 item	CDW health factor data element	x	x			
	PROMIS SF- 4 items	Patient report on CATI survey	x	x	x	x	x
Physical function	PROMIS SF- 4 item	CDW health factor data element	x	x			
	PROMIS SF-4 items	Patient report on CATI survey	x	x	x	x	x
Pain intensity	Numeric Scale (0-10)	CDW health factor data element	X	X			
Pain intensity	PEG Pain Screening Tool	Patient report on CATI survey	x	x	x	x	x
Catastrophizing	NIH recommended minimum dataset (2 items)	Patient report on CATI survey	x	X	x	X	X
Self-Efficacy	Patient Self Efficacy Questionnaire (2 items)	Patient report on CATI survey	x	X	x	X	X
Opioid exposure	NIH recommended minimum dataset - 1 item	Patient report on CATI survey	x		x		x
	At least one prescription opioid for 20 or more consecutive days	Pharmacy Benefits Management	x				x
Quality of life	Euroquol - 5 items	Patient report on CATI survey	X	x			x
Adverse clinical outcomes	(1) accidents resulting in wounds or injuries, (2) opioid-related accidents and overdose, (3) alcohol- and nonopioid drug-related accidents and overdose, (4) self-inflicted injuries and (5) violence-related injuries	CDW inpatient & outpatient Non-VA care (Fee) inpatient & outpatient (ICD codes)					x
Co-Morbidity Measures							
Sleep disturbance	PROMIS SF- 4 item	CDW health factor data element	x	x			

	PROMIS SF - 4 item	Patient report on CATI survey	x	x	x	x	x
Sedative/hypnotic exposure	At least one prescription sedative/hypnotic for 20 or more consecutive days	Pharmacy Benefits Management	x				x
PTSD symptoms	PCL-5	CDW health factor data element	x	x			x
Depressed Mood	PHQ-2 Questionnaire	Patient report on CATI survey	x	x			x
Alcohol	AUDIT-C	Patient report on CATI survey	x				
Utilization Measures							
Imaging, Providers, and Procedures	Utilization 
 - Radiographs, MRI, CT - Provider types and number - Injection, ablation, and surgery 	CDW inpatient & outpatient Non-VA care (Fee) CPT outpatient + ICD codes					x
ED visits	ED visits 
 - VA - Non-VA 	CDW inpatient & outpatient Non-VA care (Fee) inpatient & outpatient					x

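### The 30% responder rule is a percentage of a PROMIS score with an arbitrary zero, so it sets unequal bars for the two outcomes and leaves pain-interference responders sparse

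*Combined protocol and SAP*

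**What the plan says.** Under Secondary Analyses, Section 9.6 compares arms on the proportion of responders for each primary outcome. A responder "will be defined as achieving 30% improvement in pain interference or function scores at 3 months follow up". The comparison uses a mixed logit model. Patients without follow-up have their status filled in from best linear unbiased predictors (BLUPs) of the hierarchical linear model. Cumulative proportion responder graphs are planned as a sensitivity analysis on the cut point.

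The Précis and Table 10 give the instruments as four-item PROMIS short forms. Nowhere is it said whether the score is a raw sum or a standardised score.

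Section 9.2 gives the only information on scale. The standardised effects "that we are powered to detect range from 0.30 to 0.50 for the primary outcomes on the administrative sample", and "This range maps to differences of approximately 2.4 to 5.0 points in the PROMIS Pain Interference score between arms". It gives no SD as a number, no point conversion for function, no baseline mean and no expected responder rate. On correlation it says: "We assumed over time correlations of 0.50 for both patients".

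**The concern.** A percentage change is interpretable when zero on the scale means none of the thing measured. On a standardised score zero is a matter of construction, so 30% of the baseline value is a number of points set by the anchoring of the scale.

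Pain interference improves downward and function improves upward. One percentage therefore asks for different numbers of points on the two outcomes whenever their baseline means differ. Even when the means are equal, it gives different responder rates for the same true improvement.

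At stake is the tested responder comparison. If the pain-interference bar is high relative to plausible improvement, responders are few, power is low, and a finding of no difference in responders would say little.

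**Working it through.** **1. The plan's own figure.** For 8 clinics per arm and m patients per clinic, two-sided alpha 0.025, 90% power, correlation 0.50 and df = 14 - 5 = 9:

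MDES = (t[0.9875, 9] + t[0.90, 9]) x sqrt((2/8) x 2(1 - 0.50) x ((1 - ICC)/m + ICC)), where the t sum is 4.068.

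With m = 84 this gives 0.300, 0.362 and 0.504 at ICC 0.01, 0.02 and 0.05. Table 8 prints 0.30, 0.36 and 0.50, so it reproduces.

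**2. Implied SD and metric.** 2.4/0.30 = 8.0 and 5.0/0.50 = 10.0. For the survey sample, 3.0/0.37 = 8.1 and 5.5/0.55 = 10.0. If items are scored 1-5 (an assumption), a four-item sum runs from 4 to 20. Its SD cannot exceed 8, and reaches 8 only with half the patients at each extreme. An SD of 8-10 therefore points to a standardised score.

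**3. Responder rates.** Assumptions: bivariate normal scores, SD s = 8-10 for both measures and both times, r = 0.50, baseline mean mu, mean improvement d.

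- Pain interference, Y1 <= 0.7 Y0: P = Phi((d - 0.3 mu) / (s x sqrt(1 + 0.49 - 0.70))), where the root is 0.889.
- Function, Y1 >= 1.3 Y0: P = Phi((d - 0.3 mu) / (s x sqrt(1 + 1.69 - 1.30))), where the root is 1.179.

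| Baseline means (pain interference / function) | 30% in points | Pain-interference responders, d = 2.4-5 | Function responders, d = 2.4-5 |
|---|---|---|---|
| 60-65 / 35-40 | 18-19.5 / 10.5-12 | 0.8-7.2% | 15.4-32.0% |
| 50 / 50 | 15 / 15 | 3.8-13.0% | 9.1-19.8% |

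With equal means the bars coincide in points, but the rates still differ because the two roots differ. With larger improvement (d = 8-10) and pain-interference baseline 60-65, the rate is 5.3-18.4%.

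**4. Power for a true 0.30 SD difference.** There are 84 x 8 = 672 patients per arm. The design effect at ICC 0.01 is 1 + 83 x 0.01 = 1.83, so n = 672/1.83 = 367 effective per arm. Two-sided alpha is 0.05, and

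Power = Phi(|p2 - p1| / sqrt((p1(1 - p1) + p2(1 - p2))/n) - 1.96).

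- Lowest case: baseline 65, SD 8, comparison-arm improvement 3. p1 = Phi(-16.5/7.11) = 0.010, p2 = Phi(-14.1/7.11) = 0.024, power 0.29.
- Highest case: baseline 60, SD 10, comparison-arm improvement 5. p1 = Phi(-13/8.89) = 0.072, p2 = Phi(-10/8.89) = 0.130, power 0.75.
- Same two SD and improvement settings at baseline 50: 0.046 against 0.088 (power 0.64) and 0.130 against 0.215 (power 0.86).
- Function, baseline 37.5: 0.70-0.76.
- A 5-point cut, used only as a comparator. The SD of change is s x sqrt(2(1 - 0.50)) = s. With improvement 5 and SD 10, p1 = 0.500, p2 = Phi(0.3) = 0.618, power about 0.90. The other settings also give about 0.90.

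**5. The BLUP fill-in.** Leaving out covariates and clinic effects, a missing pain-interference value is predicted as mu - d + 0.5(Y0 - mu). It meets the 30% rule only if Y0 >= (0.5 mu - d)/0.2. For mu = 60, d = 8 this is 22/0.2 = 110. For mu = 65, d = 3 it is 29.5/0.2 = 147.5. The lower figure is already 50 points, or 5 SD at SD 10, above the mean. Nearly all of the 20% assumed lost to follow-up would be classed as non-responders.

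**The case against.** The strongest reply is that the documents do not supply the numbers that make the rule look bad. They name no T-score and give no baseline mean or function SD. The SD of 8-10 is back-calculated and applies to pain interference only. That stands, and it is why the rates above are conditional.

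If a raw sum were intended, these rates would not apply. The rule would still take a percentage of a score whose minimum is 4, not 0, under the 1-5 assumption.

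The analysis is secondary. The primary model uses the continuous scores. Section 9.3 commits to reading all outcomes against literature on meaningful change, and Section 9.6 cites a source for the 30% and plans graphs across cut points. All of this limits the damage. The tested logit model still uses the 30% cut.

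A reader might infer more than the documents support:

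- That the rule demands a 2 SD fall in pain interference. This needs an assumed baseline near 60-65; at 50 it is 15/10 to 15/8, or 1.5-1.9 SD.
- That the comparison is nearly empty. At d = 8-10 the rate reaches 5-18%, and for a 0.50 SD difference power is 72% or more at baseline 60-65.
- That mild patients cannot reach the pain-interference target. This needs the instrument's floor score, which is not given.
- That the rule runs backwards for both measures. For pain interference, milder patients need fewer points. Only for function do better-functioning patients need more.
- That 5 points is the plan's own responder threshold. In Section 9.2 it is the top of a range of detectable differences between arms, not a within-patient change.

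**Conclusion.** The concern holds in a limited form. The 30% rule is undefined as to metric, and on the metric that Section 9.2 implies it depends on an arbitrary origin. It gives unequal responder rates for equal true improvement: about 1-7% against 15-32%, or 4-13% against 9-20% when both baseline means are 50. Pain-interference responders would be sparse, with about 30-75% power where a 5-point cut would have about 90%.

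These sizes rest on the assumed baseline means, SD 8-10 for both measures, normality and mean improvement of 2.4-5 points (3-5 in the comparison arm for power). The power figures also assume that ICC 0.01 applies to the binary outcome. The dependence on the origin and the missing metric do not rest on the assumed means. The primary test is unaffected, and the change is worth making before analysis.

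**What to change.** In Section 9.6, state the score metric. In the logit model, replace the 30% rule with a prespecified within-patient change in points for each outcome: a fall in pain interference and a rise in function. Take each value from a cited source on meaningful within-patient change. Section 9.2 already cites a source on clinically relevant differences for pain interference; it gives no counterpart for function.

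Fix the values before any outcome comparison by arm. Section 6.3 says the study statisticians are unblinded, so timing relative to unblinding is no safeguard here. Keep the cumulative graphs. If wanted, report the 30% rule as a sensitivity analysis.

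The cost is analysis-plan wording and a literature justification, with no new data. The downside is that a low cut labels some patients with no true improvement as responders. At 5 points with zero mean improvement this is Phi(-5/8) to Phi(-5/10), about 27-31%.

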9.2.1 Treatment Assignment Procedures

In this study, randomization occurs at the clinic (i.e., the cluster) level and we plan on conducting a covariate constrained randomization²⁻⁴ with the following clinic level covariates assessed prior to randomization: 1) average pain scale scores of LBP patients at clinic, 2) average level of opioid exposure of LBP patients at clinic, 3) number of participating primary care providers at clinic, 4) clinic location (main medical center/community clinic) and 5) average age of LBP patients at clinic. These characteristics were chosen to represent factors likely to be associated with baseline differences in patient population that may affect primary outcomes. However, the exact number of covariates we use will depend on the quality and distribution of these covariates across the 16 clinics that we enroll. For example, if all the clinics we enroll are community clinics, then we would drop the clinic location covariate in the randomization.

Currently, throughout the VA, general pain scale scores (rate pain on a scale from 1 to 10) are being collected for all primary care visits and stored in administrative data. Our plan will be to use these data, averaging the pain scale scores of LBP Veterans at each clinic over a 3 to 6-month time period prior to clinic enrollment. For Durham primary care clinics, we found that pain scores were collected at over 95% of primary care visits for lower back pain over a one-year time period. From the [name] et al. pilot study³³ of Veterans with back pain (n=50), we found that correlation of pain scale scores to PROMIS pain interference at baseline was approximately 0.55, a reasonably strong correlation. For the opioid exposure covariate, our plan is to apply the PMC3 opioid exposure definition to LBP patients at clinics over a 3 to 6-month period prior to clinic enrollment and then use the proportion of patients that meet the opioid exposure definition as the average level of opioid exposure for the clinic. The number of participating (referring) providers at a clinic will be used as an indication of size of clinic (volume of patients served). For the age of LBP patients, we will use age that is available in the electronic health record and average the age of Veterans with LBP visits to the clinic over the 3 to 6-month time period prior to clinic enrollment.

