$\beta_1^*(\text{moderator}) + \beta_2^*(\text{moderator}^*\text{intervention}) + \beta_3^*(\text{followup}) + \beta_4^*(\text{followup}^*\text{intervention}) + \beta_5^*(\text{moderator}^*\text{followup}) + \beta_6^*(\text{moderator}^*\text{intervention}^*\text{followup})$ for clinic i , patient j , at time k . A random effects (clinics and time by clinics) will be included in the model to account for clustering of patients within clinics, as the clinics are the unit of randomization. Differential change in pain interference or function by moderator for the two intervention groups is supported if the coefficient for β_6 is significantly different than zero at the $p=0.025$ level. For the adherence multinomial outcome, we will fit a generalized linear model with a random effect for clinic and cumulative logit link function. As the adherence outcome is potentially a 3-level outcome there will be two interaction terms to examine for moderation effects (e.g. whether the effect of the intervention by chronicity is different for those moderately adherent vs. not adherent and/or those fully adherent vs. not adherent).

Exploratory analyses to identify multidimensional subgroups from combinations of baseline characteristics (e.g. age, sex, opioid use) for treatment moderation of the primary outcomes of pain and function as well as per protocol adherence to treatment.

Patients are likely to vary in treatment response. This variation is known as heterogeneity of treatment effects (HTE). Exploration of HTE has typically focused on one-factor-at-a-time post-hoc subgroup analyses (as described in our planned subgroup analysis); however, it is possible to instead identify multidimensional subgroups exhibiting HTE. In particular, we will apply the data-driven method GUIDE⁶⁶(Generalized, Unbiased, Interaction Detection and Estimation) that can be used for longitudinal outcomes, so can incorporate all follow-up outcomes at 3 and 12-months, as well as multi-response outcomes. GUIDE uses a regression tree algorithm that identifies subgroups with heterogeneous effects and estimates how the treatment effect varies across the subgroups. We will include baseline demographic (e.g. age, sex, race) and clinical characteristics (e.g. LBP chronicity, opioid use, comorbid conditions) that are available from EHR. GUIDE provides bootstrap confidence intervals for the treatment effects of identified nodes and is available via a software package.

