Missing Data. We do not anticipate much missing data in the main predictors of interest, intervention arm and patient characteristics available in the EHR or assessed at baseline in survey outcomes. There may be missing values in the outcome measures due to dropout, death, a missed interim assessment or assessment outside 1-month window for 3-month follow-up, or item non-response. However, hierarchical linear mixed models via maximum likelihood estimation, our main analysis technique for the primary outcomes, implicitly accommodate missingness at random (MAR).⁵⁵ Therefore, inferences will be valid even with differential dropout by intervention arm. We will thoroughly explore reasons for dropout, and depending upon the type and scope of missing data, we may explore the sensitivity of intervention effects to different missing data mechanisms (MAR vs. MNAR).⁶⁹ Our plan would be to conduct sensitivity analyses to evaluate the sensitivity of the assumption of MAR and/or MNAR on intervention effects. If our primary model included design variables only (treatment, stratification variables, clinic) this model would meet the MAR assumptions if missing data is related to previous outcome assessments or design variables included in the primary model. We can assess the sensitivity of the MAR assumption by conducting an analysis that includes auxiliary variables (either as additional variables in primary models or by conducting a multiple imputation including auxiliary variables). These auxiliary variables or other baseline characteristics for the large sample may be limited due to availability in the EHR. We are currently proposing to include age,

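### Secondary responder analysis: assigning missing responder status from a single BLUP biases the responder proportions, and the option to condition on clinic cannot estimate an arm effect

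*Combined protocol and SAP*

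**What the plan says.** The secondary analyses in section 9.6 open with "We will assess differences in proportions of" responders in the two arms, for each primary outcome. A responder is a patient whose pain interference or function score improves by 30% at 3 months. For patients without a 3-month score, "Responder status for those missing outcome data will be estimated using best linear unbiased predictors" from the hierarchical linear model, so that they stay in the analysis. The arms are then compared in a logit mixed model whose main predictor is "treatment arm adjusting for clustering of VA clinic either with random effects or by conditioning". The chronic-opioid model includes "baseline opioid use status (chronic or not chronic) adjusting for clustering of VA clinic either with random effects or by conditioning".

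Three other statements bear on this:

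- Section 9.2.1: "In this study, randomization occurs at the clinic (i.e., the cluster) level".
- Section 9.6, Missing Data, lists among the sources of missing outcomes "a missed interim assessment or assessment outside 1-month window for 3-month follow-up". Of the likelihood-based mixed model it says: "Therefore, inferences will be valid even with differential dropout by intervention arm".
- The same subsection plans multiple imputation of outcomes to examine the missing-at-random (MAR) assumption, respecting clustering if needed. It does not connect this to responder status.

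The only sensitivity analysis given for responders varies the cut point.

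**The concern.** A best linear unbiased predictor (BLUP) for a patient with only a baseline score estimates the mean outcome of similar patients. Individual outcomes scatter widely around that mean, and the scatter decides who crosses a threshold. If the mean improvement is well short of 30%, nearly every prediction falls on the non-responder side, although some of these patients would have responded. If it is above 30%, the error reverses. The validity claim for the mixed model concerns the continuous score and does not carry over to a dichotomised prediction. The assigned statuses are also analysed as if observed, so their uncertainty is not counted.

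The stake is the responder proportions and, under some conditions, the comparison between arms. Unlike a model that fails to converge, this error would leave no sign in the output.

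The clinic adjustment is a separate defect. A clinic delivers one pathway only, so any method that compares patients within clinics has no information about arm.

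**Working it through.** **Inputs from the documents.** Correlation over time 0.50, attrition 20%, 105 patients at baseline in each of 16 clinics (section 9.2). The attrition figure reproduces: 84/0.80 = 105 and 105 × 16 = 1,680, so 0.20 × 1,680 = 336 patients lack a 3-month score. The SD of pain interference implied by section 9.2 is 2.4/0.30 = 8 to 5.0/0.50 = 10 points.

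**Assumptions.** The documents give no baseline mean, mean improvement, scoring metric, responder rate or arm-specific missing rate. These are assumed and varied. Scores are taken as bivariate normal with equal SD σ, and missingness as at random.

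**Step 1: spread around the cut.** For pain interference a responder has Y1 ≤ 0.7·Y0.

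- Real outcomes: SD of Y1 − 0.7·Y0 = σ√(1 + 0.49 − 2 × 0.7 × 0.5) = σ√0.79 = 0.889σ.
- BLUP: SD = |0.5 − 0.7|σ = 0.20σ.

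For physical function the factor is 1.3, giving σ√(1 + 1.69 − 1.3) = 1.18σ for real outcomes and 0.80σ for the BLUP. The distortion is therefore milder.

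**Step 2: responders among missing patients, pain interference.** With baseline 60, SD 10 and improvement 8, the mean is 52 and the cut is 42, a distance of 10 points.

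- Expected: Φ(−10/8.89) = 13.0%, or 44 of 336.
- BLUP rule: Φ(−10/2) = 0.0%.

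At a given true rate p the mean and SD cancel, and the rule gives Φ(z(p) × 0.889/0.20):

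| True rate among missing | 10% | 20% | 30% | 40% | 50% | 60% |
|---|---|---|---|---|---|---|
| BLUP rule | 0.0% | 0.0% | 1.0% | 13.0% | 50.0% | 87.0% |

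At 50% the proportion is unbiased, but about 40% of missing patients are still misclassified.

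Over baselines of 50–70 and improvements of 2.4–10 points, the rule gives 0–0.6% where 0.4–29% is expected. With a correlation of 0.3 it gives up to 10.6% (expected up to 31%). If covariates explained 10% of residual variance, it would give up to 7.0%. For physical function (assumed baseline 34–42, improvement 2.4–8) it gives 6–39% against 14–43%.

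**Step 3: unequal missingness, no true effect** (baseline 60, SD 10, improvement 8 in both arms). The arm proportion is (1 − m) × 13.0% + m × 0.0%.

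| Missing by arm | Proportions | Odds ratio (true value 1) |
|---|---|---|
| 10% v 30% | 11.7% v 9.1% | 0.76 |
| 15% v 25% | 11.1% v 9.8% | 0.87 |
| 18% v 22% | 10.7% v 10.2% | 0.95 |

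For physical function the odds ratio is 0.86–0.97 at 10% v 30%.

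**Step 4: equal 20% missingness, true effect present** (baseline 60, SD 10).

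| Mean improvement | True difference, odds ratio | BLUP rule |
|---|---|---|
| 5 v 10 points | 11.2 points, 2.92 | 9.0 points, 2.83 |
| 12 v 17 points | 20.5 points, 2.51 | 22.6 points, 2.96 |
| 14 v 19 points | 21.8 points, 2.47 | 30.9 points, 3.73 |

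**Step 5: does imputation repair it?** The check was 1,000 simulated trials per scenario (8 clinics per arm, 105 per clinic, ICC 0.02, 20 imputations). With 10% v 30% missing and no effect, the BLUP rule gave an odds ratio of 0.75 and imputation 1.00. With 14 v 19 points and equal missingness, complete data gave 32.7% v 54.4% (odds ratio 2.46), the BLUP rule 27.0% v 56.9% (3.57) and imputation 32.6% v 54.4% (2.46). The imputations drew residuals but not parameter uncertainty, so this tests the bias and not the interval width.

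**Step 6: conditioning on clinic.** Sixteen clinic indicators have rank 16; adding arm as a 17th column leaves the rank at 16. The clinic-conditional logistic log-likelihood is the same (−1027.14106, on simulated data) at arm coefficients 0, 0.5 and 1.0. Arm cannot be estimated. This reads conditioning as fixed clinic effects or a clinic-stratified conditional likelihood, since the plan does not define the term.

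**The case against.** The strongest reply is that little changes in the test the plan specifies. That test is a logit model. With equal missingness and improvement well short of 30%, the odds ratio hardly moves: 2.92 to 2.83 above, and a 1–4% fall in the log odds ratio across the range examined. With equal missingness and no true effect, the contrast is unbiased. The large distortions need either 10% v 30% missing, which the plan does not predict, or mean improvements of 14–19 points, which is 1.4–1.9 SD at SD 10. The plan also monitors the timing of follow-up assessments in both arms, and at 18% v 22% the false difference is under one percentage point. Finally, multiple imputation is already mentioned, random effects are the first-listed clinic adjustment, and all this is secondary.

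Most of that stands and limits the severity. The 10% v 30% and 14 v 19 point cases are stress cases. The reply does not rescue the rule, however. The section says proportions will be compared, and those are wrong whenever the responder rate differs from 50%. Section 9.6 itself contemplates dropout that differs by arm, and different staff collect the 3-month score in the two pathways (section 9.5.1). The planned imputation explores MAR and is not tied to responder status, for which the text names the BLUP rule. On clinic adjustment, the Aim 2 adherence model already specifies the workable choice: "we will fit a generalized linear model with a random effect for clinic and cumulative logit link function".

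**Conclusion.** Both points hold, for secondary analyses only. The primary mixed model and the sample size are unaffected.

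The BLUP rule would set the status of about 336 of 1,680 patients at the planned attrition. For pain interference at modest improvement, it would class almost none of them as responders. The arm contrast depends on conditions that the documents do not settle:

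- missingness differing by arm creates a false difference;
- equal missingness with modest improvement shrinks the difference in proportions by about a fifth and leaves the odds ratio nearly intact;
- equal missingness with an arm near 30% improvement inflates both scales.

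The direction of the misclassification follows from the rule and the plan's correlation. Its size rests on the assumed baseline, improvement and missing rates. Physical function is affected less. This should be changed, but it does not threaten the main conclusion.

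The conditioning option would fail visibly if used, so that part is a wording correction.

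**What to change.** In the secondary analyses of section 9.6:

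1. Replace the BLUP sentence. State that the continuous 3-month score is multiply imputed with a method that respects clinic clustering, that responder status is derived within each imputed data set, and that the responder model is fitted in each set and the results pooled. The Missing Data text makes cluster-aware imputation conditional on need; for this analysis it should be a commitment.
2. Delete the conditioning alternative from both the responder model and the chronic-opioid model, leaving random clinic effects.

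The 30% definition and the cumulative responder graphs can stay.

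The cost is two wording changes and modest programming, because imputation is already planned. Intervals should widen somewhat once imputation uncertainty is counted; the amount was not calculated. Data collection, sample size and the primary analysis do not change.
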